8.6 Health Economics OR Medical Resource Utilization and Health Economics

Health Economics/Medical Resource Utilization and Health Economics parameters will not be evaluated in this study.

9 STATISTICAL CONSIDERATIONS

9.2 Populations for Analyses

For purposes of analysis, the following analysis sets will be used in this study:

Enrolled Population: All subjects who sign informed consent.

Full Analysis Set (FAS): All subjects who were randomized. Following the intent-to-treat principle, subjects will be analyzed according to the treatment group assigned at randomization. The FAS will be the primary efficacy analysis population.

Per Protocol Set (PPS): A subset of the FAS who are compliant with study treatment and who do not have any relevant protocol deviations that may impact the coprimary efficacy endpoint assessments (Section 9.6.3). The PPS will be analyzed for the coprimary endpoint comparisons according to the treatment assigned at randomization.

As-treated Population: All randomized subjects who took at least one dose of study treatment. Subjects will be analyzed according to treatment received. The As-treated population will be for safety analyses.

9.3 Endpoints

9.3.1 Primary Endpoints

[figure not shown]
The coprimary efficacy endpoints for BMS-986165 compared to placebo at Week 16 are defined as:

- sPGA 0/1 response assessed as a proportion of subjects with a sPGA score of 0 or 1
- PASI 75 response assessed as a proportion of subjects who achieve a 75% improvement from baseline in the PASI score

9.3.2 Key Secondary Endpoints

The key secondary endpoints for BMS-986165 compared to placebo at Week 16 are defined as:

- PASI 90 response assessed as a proportion of subjects who achieve a 90% improvement from baseline in the PASI score
- sPGA 0 response assessed as a proportion of subjects with a sPGA score of 0
- PASI 100 response assessed as a proportion of subjects who achieve a 100% improvement from baseline in the PASI score
- Change from baseline in PSSD symptom score
- PSSD symptom score of 0 assessed as a proportion of subjects with a PSSD symptom score of 0 among subjects with a baseline PSSD symptom score ≥ 1
- ss-PGA 0/1 assessed as a proportion of subjects with a ss-PGA score 0 or 1 among subjects with a baseline ss-PGA score ≥ 3
- DLQI 0/1 assessed as a proportion of subjects with a DLQI score of 0 or 1 among subjects with a baseline DLQI score ≥ 2
- PGA-F 0/1 assessed as a proportion of subjects with a PGA-F score of 0 or 1 among subjects with a baseline PGA-F score ≥ 3
- pp-PGA 0/1 assessed as a proportion of subjects with a pp-PGA score of 0 or 1 among subjects with a baseline pp-PGA score ≥ 3

9.4 Efficacy Analyses

Categorical data will be summarized as frequency counts and percentages. Continuous data will be summarized using n, mean, standard deviation, median, minimum, and maximum unless otherwise specified. Efficacy values will be summarized for all visits in which the variable is assessed. Details of the planned analyses of endpoints during the 16-week double-blind placebo-controlled period will be documented in the statistical analysis plan (SAP) and finalized before the Week 16 database lock.

During the first 16 weeks of treatment, data will be presented for the following treatments:

- BMS-986165 6 mg QD
- Placebo

After Week 16, data will be presented for the following treatments:

- BMS-986165 6 mg QD
- Placebo → BMS-986165 6 mg QD (starting from Week 16 through Week 52)
- All BMS-986165 6 mg QD (all subjects exposed to BMS-986165 6 mg QD; includes subjects on placebo that switched to BMS-986165 6 mg QD)

9.4.1 Coprimary Endpoint Analyses

The analysis model for the coprimary efficacy endpoints, sPGA 0/1 and PASI 75 (responder/nonresponder) at Week 16, will use stratified Cochran-Mantel-Haenszel (CMH) tests stratified by the stratification factors used for randomization (see [Section 4.1.2](#)) to compare the response rates of BMS-986165 6 mg QD to placebo using the Week 16 data of the FAS. The odds ratio (ratio of odds in BMS-986165 6 mg QD group to the odds in placebo group) and the corresponding 2-sided 95% confidence interval (CI) will be provided. Estimates of proportions and their 2-sided 95% CIs will be provided.

9.4.1.1 Imputation Methods for Coprimary Endpoints

Non-responder imputation (NRI) will be used for coprimary efficacy endpoints for subjects who discontinue treatment or study prior to Week 16, start a protocol prohibited medication/therapy that could improve psoriasis during the first 16 weeks of treatment, or who have otherwise missing endpoint data at the specified timepoint. NRI will be the primary method of imputation for the coprimary efficacy endpoints.

9.4.1.2 Sensitivity Analyses for the Coprimary Endpoints

Sensitivity analyses to be performed for the coprimary endpoints will be described in the SAP prior to the Week 16 database lock.

9.4.1.3 *Supportive Analyses for the Coprimary Endpoints*

The coprimary efficacy endpoints will be analyzed using the Week 16 data of the PPS using the analysis described in [Section 9.4.1](#) and the imputation methods described in [Section 9.4.1.1](#).

Additionally, the coprimary efficacy endpoints for the FAS will be analyzed with a logistic regression model with treatment and the stratification factors used for randomization as covariates.

9.4.1.4 *Subgroup Analyses for the Coprimary Endpoints*

Subgroup analyses will be conducted for the coprimary efficacy endpoints for the FAS using the analysis described in [Section 9.4.1](#) and the imputation methods described in [Section 9.4.1.1](#). Subgroups to be evaluated may include the following:

- Gender
- Age categories (<65; \geq 65)
- Prior biologic use (yes/no)
- Prior systemic treatment of psoriasis (yes/no)
- Country

Additional subgroups may be defined for descriptive summaries in the SAP.

9.4.2 *Secondary Endpoint Analyses*

The analysis model for the binary secondary endpoints will use stratified CMH tests stratified by the stratification factors used for randomization (see [Section 4.1.2](#)) to compare the response rates of BMS-986165 6 mg QD to placebo for the FAS. The odds ratio (ratio of odds in BMS-986165 6 mg QD group to the odds in placebo group) and the corresponding 2-sided 95% CI will be provided.

The analysis model for continuous secondary endpoints will use analysis of covariance (ANCOVA) with treatment and stratification factors used for randomization as fixed effects. The baseline value will be added into the model as a covariate. Treatment differences based on least-squares (LS) means and the corresponding 2-sided 95% CIs will be provided for the difference between BMS-986165 6 mg QD and placebo.

[figure not shown]
9.4.2.1 *Imputation Methods for Secondary Endpoints*

The NRI will be applied to the analyses of binary secondary efficacy endpoints for subjects who discontinue early, start a protocol prohibited medication/therapy that could improve psoriasis, or who have otherwise missing endpoint data prior to the specified timepoint.

For continuous secondary efficacy endpoints, a modified baseline observation carried forward (mBOCF) will be used for missing data. The baseline observation will be carried forward for subjects who discontinue study treatment due to:

- Lack of efficacy
- AEs

and for subjects who start a protocol prohibited medication/therapy that could improve psoriasis prior to the endpoint. The last valid observation will be carried forward for all other subjects with missing data.

9.5 Safety Analyses

Safety data will be analyzed for AEs, SAEs, laboratory analytes, vital signs, ECGs, and suicidality and depression. Safety will be summarized using the As-treated population. Categorical data will be summarized as frequency counts and percentages. Continuous data will be summarized using n, mean, standard deviation, median, minimum, and maximum unless otherwise specified.

During the first 16 weeks of treatment data will be presented for the following treatments:

- BMS-986165 6 mg QD
- Placebo

After Week 16 data will be presented for the following treatments:

- BMS-986165 6 mg QD
- Placebo→BMS-986165 6 mg QD (starting from Week 16 through Week 52)
- All BMS-986165 6 mg QD (all subjects exposed to BMS-986165 6 mg QD; includes subjects on placebo that switched to BMS-986165 6 mg QD)

9.5.1 Adverse Events

Treatment-emergent adverse events (TEAEs), SAEs and deaths, and AEs leading to study treatment discontinuation, AEs by maximum severity, and AEs by relationship will be summarized by the MedDRA system organ class and preferred term. All TEAEs, AEIs, as well each AE adjudicated category (ie, infections, cardiovascular, and suicidal ideation and behavior) will also be summarized by preferred term sorted by decreasing frequency.

9.5.2 Vital Signs and ECGs

Vital signs and ECGs will be summarized as raw, change from baseline, and change from maximum postbaseline value. Incidence of abnormal ECG will also be summarized.

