2) Total bilirubin >2 times ULN, without initial findings of cholestasis (elevated serum alkaline phosphatase),

AND

3) No other immediately apparent possible causes of liver function test elevation and hyperbilirubinemia, including, but not limited to, viral hepatitis, pre-existing chronic or acute liver disease, or the administration of other drug(s) known to be hepatotoxic.

8.2.9 *Other Safety Considerations*

Any significant worsening of a pre-existing medical condition noted during interim or final physical examinations, electrocardiogram, x-ray filming, any other potential safety assessment required or not required by protocol should also be recorded as a nonserious or serious AE, as appropriate, and reported accordingly.

8.3 *Overdose*

For this study, taking more than 2 days' worth of study medication within a 24-hour time period will be considered an overdose.

In the event of an overdose the investigator should:

- 1) Contact the Medical Monitor immediately
- 2) Closely monitor the subject for AEs/SAEs and laboratory abnormalities

Decisions regarding dose interruptions or modifications will be made by the investigator in consultation with the Medical Monitor based on the clinical evaluation of the subject.

8.4 *Safety*

Planned time points for all safety assessments are listed in the Schedule of Activities ([Section 1.3](#)).

8.4.1 *Physical Examinations*

A complete physical examination will include general appearance, vital signs, eyes, ears, nose, mouth, throat, neck, respiratory, cardiovascular, respiratory, GI, lymphatic, musculoskeletal, skin, psychiatric and neurologic exams. A targeted physical examination will include vital signs, and any organ system associated with an AE or a laboratory abnormality.

8.4.2 *Vital Signs*

Refer to Schedule of Activities ([Section 1.3](#)).

8.4.3 *Electrocardiograms*

A 12-lead ECG will be performed at the visits indicated in the Schedule of Activities ([Section 1.3](#)). The patient will remain supine for 5-10 minutes prior to the ECG and must have their lab work done after the tracing so that the ECG results remain as accurate as possible. The ECG results will be read by the primary study investigator or a designee.

8.4.4 *Tuberculosis Screening and Chest Imaging*

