4.2 Safety

The safety outcomes include the following:

- Adverse events (AEs)
 - Treatment-emergent adverse events (TEAEs) – defined as:
 - AEs which occur after the first dose of study treatment through 30 days after the final dose of the study treatment;
 - Treatment-emergent adverse events of interest (AEIs) for the following events:
 - Skin-related AEs
 - Infection AEs, including influenza
 - Creatine kinase (CK) elevation (evaluated as lab toxicity grade 2 or higher)
 - Malignancy
 - SAEs
 - Deaths
- Clinical laboratory parameters

Sponsor: Bristol-Myers Squibb

Protocol no: IM011065

- Absolute and change from baseline values
- Laboratory abnormalities (as determined by Controlled Terminology Criteria for Adverse Events [CTCAE v5.0] grading) presented as the worst postbaseline toxicity group
- Shifts from baseline to maximum postbaseline value
- Potential drug induced liver injury (DILI) is defined as a subject who meets the following criteria:
 - 1) ALT or AST elevation >3 times ULN

AND

 - 2) Total bilirubin >2 times ULN, without initial findings of cholestasis (elevated serum alkaline phosphatase)

AND

 - 3) No other immediately apparent possible causes of liver function test elevation and hyperbilirubinemia, including, but not limited to, viral hepatitis, preexisting chronic or acute liver disease, or the administration of other drug(s) known to be hepatotoxic.
- ALT or AST elevation >5 times ULN
- Vital signs
 - Absolute and change from baseline values
 - Marked abnormalities defined by the below categories:
 - Heart rate:
 - Value > 100 and change from baseline > 30
 - Value < 55 and change from baseline < -15
 - Systolic blood pressure:
 - Value > 140 and change from baseline > 20
 - Value < 90 and change from baseline < -20
 - Diastolic blood pressure:
 - Value > 90 and change from baseline > 10
 - Value < 55 and change from baseline < -10
- Electrocardiograms (ECGs)
 - Absolute and change from baseline values
 - Marked abnormalities defined by the below categories:
 - QT interval corrected using Fridericia's formula (QTcF):

Sponsor: Bristol-Myers Squibb
Protocol no: IM011065

- 450 -< 480 msec
- 480 -< 500 msec
- ≥ 500 msec
- $30 < \text{change from baseline} \leq 60$ msec
- Change from baseline > 60 msec
- Males: < 450 msec, ≥ 450 msec
- Females: < 470 msec, ≥ 470 msec
- PR interval ≥ 200 msec
- QRS interval ≥ 120 msec

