6.2.5 ECGs

ECG parameters will be summarized by time point, as applicable. The following summaries will be provided for each parameter:

- Absolute, change from baseline values and change from baseline in maximum post-baseline value for continuous parameters
- Number and percentage of subjects for the following:
 - Marked abnormality for each abnormality category as defined in Section 4.2

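### SAP 4.2 and 6.2.5 count PR, QRS and absolute QTcF abnormalities without reference to baseline, so the table gives prevalence where Protocol 9.5.2 promises incidence

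*Protocol*

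**What the plan says.** Protocol 9.5.2 plans raw and change summaries for ECGs and adds "Incidence of abnormal ECG will also be summarized". It does not define abnormal. Protocol 8.4.3 says of the tracings: "The ECG results will be read by the primary study investigator or a designee".

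SAP 6.2.5 sets the general rule "ECG parameters will be summarized by time point, as applicable". It then lists two outputs: continuous summaries (absolute value, change from baseline, and change from baseline in the maximum post-baseline value), and numbers and percentages of subjects with "Marked abnormality for each abnormality category as defined in Section 4.2".

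The ECG categories in SAP 4.2 are:
- absolute QTcF bands (450 to under 480, 480 to under 500, and 500 msec or more) and splits at 450 msec for males and 470 msec for females;
- QTcF change categories (over 30 up to 60 msec, and "Change from baseline > 60 msec");
- "PR interval ≥ 200 msec";
- "QRS interval ≥ 120 msec".

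The QTcF change categories stand on their own and are not joined to the absolute bands. PR and QRS have no change category. No ECG shift table is listed.

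**The concern.** Incidence means new occurrence. A count of everyone over a threshold at a visit, with no regard to where they started, is prevalence. Under the SAP rule, a hypothetical subject with PR 210 msec at Week 0 and 210 msec at Week 16 is a marked abnormality at Week 16.

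Such subjects can be in the trial. Exclusion criterion 5(b) in Protocol 5.2 removes only ECG abnormalities that are both clinically significant and an unacceptable risk.

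The placebo-controlled evidence is thin. Protocol Table 2 schedules ECGs at Week 0 and Week 16 only, so there is one planned post-baseline tracing while the placebo arm is still on placebo. The later ECGs, at Weeks 24 and 52 (Protocol Table 3), have no placebo comparator. At stake is whether a reader can see, by arm, how many subjects became newly abnormal on PR or QRS.

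**Working it through.** **Comparison within the SAP.** The other safety data are related to baseline at subject level:

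| Data | How abnormality is tied to baseline |
|---|---|
| Vital signs (4.2) | Every category joins a value to a change, e.g. "Value > 100 and change from baseline > 30" |
| Laboratory (4.2, 6.2.3) | Shift from baseline to maximum post-baseline |
| PHQ-8, eC-SSRS (6.2.6) | Shifts from baseline |
| QTcF change (4.2) | Change categories, separate from the absolute bands |
| QTcF absolute, PR, QRS (4.2) | None |

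**Size.** The documents state no figure on this point, so there is none to reproduce. What follows is an illustration.

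Inputs:
- N = 219 at 2:1 (Protocol 4.2), so 146 and 73.
- q = baseline prevalence of a persistent abnormality, assumed 2%, 5% or 10%, equal in both arms and fully persistent.
- r = new-onset rate among subjects normal at baseline, assumed 6% on BMS-986165 and 2% on placebo.

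Formulas:
- Counted rate with no baseline condition = q + (1 − q) × r.
- Expected risk difference = (1 − q) × (6% − 2%).
- Unchanged subjects counted = 146q and 73q.

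Example at q = 5%: 0.05 + 0.95 × 0.06 = 10.7%; 0.05 + 0.95 × 0.02 = 6.9%; ratio 10.7/6.9 = 1.55; difference 0.95 × 4.0 = 3.8 points.

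| q | Unchanged subjects counted (active / placebo) | Counted rates | Ratio | Difference (points) |
|---|---|---|---|---|
| 0% (true incidence) | 0 / 0 | 6.0% vs 2.0% | 3.0 | 4.0 |
| 2% | 2.9 / 1.5 | 7.9% vs 4.0% | 1.99 | 3.9 |
| 5% | 7.3 / 3.7 | 10.7% vs 6.9% | 1.55 | 3.8 |
| 10% | 14.6 / 7.3 | 15.4% vs 11.8% | 1.31 | 3.6 |

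The share of counted cases that are pre-existing is q divided by the counted rate: 25%, 47% and 65% on BMS-986165, and 51%, 72% and 85% on placebo.

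Pre-existing cases also add noise. The standard deviation of the arm difference from them alone is √[q(1 − q)(1/146 + 1/73)] = 2.0, 3.1 and 4.3 points at q = 2%, 5% and 10%. In a single trial, a chance imbalance at baseline can therefore be about as large as the assumed effect, and the table gives no means of separating the two.

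**The case against.** The strongest reply is that the protocol leaves abnormal ECG undefined, and making such a term operational is the SAP's job. That largely stands. A reader might infer that the SAP breaks a promise to tabulate the investigator's reading, so that rhythm and morphology findings go uncounted. The documents do not support this:
- Protocol 8.4.3 says who reads the tracing and does not make the reading a planned summary.
- Clinically significant ECG results meet the AE definition (Protocol Appendix 3).
- Reported dysrhythmias and heart blocks go to blinded cardiovascular adjudication (Protocol 4.1.6.3), and adjudicated events are summarized (Protocol 9.5.1, SAP 6.2.1.1).
- What falls outside is findings judged not clinically significant.
- Four bullets of SAP 2.5 are redacted, so one cannot say that the choice went unrecorded.

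The SAP also does not ignore change. A stable PR of 210 msec contributes zero to the continuous change summaries, and QTcF has its own change categories. A baseline row, if shown, and the placebo arm would reveal the background rate by group. But none of these shows how many individual subjects crossed a PR or QRS threshold.

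A reader might also infer that the method hides a drug effect in absolute terms. It does not do so in expectation, because randomization balances pre-existing cases. Take 5% prevalence with 3 new cases on drug and none on placebo. The expected table is (7.3 + 3)/146 = 7.1% against 3.65/73 = 5.0%, a difference of 2.1 points. The emergent count is 3/138.7 = 2.2% against 0. Rounding the pre-existing cases to 7 and 4 would give 6.8% against 5.5%, but that smaller gap comes from the rounding.

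**Conclusion.** The point holds for PR, QRS and the absolute QTcF bands. As written, the SAP table reports prevalence by visit, which is not the incidence that Protocol 9.5.2 names, and it is out of line with how the same SAP treats vital signs, laboratory data, PHQ-8 and eC-SSRS. The gap is widest for PR and QRS, which have no categorical measure of change, and narrower for QTcF.

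In the illustration the ratio between arms falls from 3.0 to between 1.99 and 1.31, while the expected risk difference stays within 0.4 points of 4.0. These figures rest on assumed prevalence, full persistence and assumed new-onset rates, none of which the documents give.

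The tables are descriptive. No efficacy endpoint, power or Type I error is affected. This is a modest but worthwhile correction to a safety table.

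**What to change.** In SAP 4.2 and 6.2.5, present the PR, QRS and absolute QTcF categories as shift tables from baseline to worst post-baseline value, by arm, for Weeks 0-16. Alternatively, count each category only among subjects below that threshold at baseline and state that denominator. Both use interval data already planned for summary.

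The cost is SAP wording and one or two extra tables. With the second option, the denominator loses subjects who were abnormal at baseline; the shift table keeps them in view.

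If the eCRF records the investigator's overall ECG reading, tabulate it the same way. This part is conditional, because the documents do not show such a field. If there is none, a sentence stating that the SAP 4.2 categories are the working definition of abnormal ECG would settle the term.

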9.5.3 Clinical Laboratory Tests

Laboratory analytes will be summarized as raw, change from baseline, and change from maximum postbaseline value. Incidence of abnormal, high, or low values will be summarized.

9.5.4 Suicidality and Depression Assessments

Suicidality and depression will be assessed using eC-SSRS and PHQ-8. Data will be summarized, as applicable.

9.6 Other Analyses

9.6.1 Demographics and Baseline Data

Demographics and baseline data will be summarized by treatment for each applicable analysis population. Categorical data will be summarized as frequency counts and percentages. Continuous data will be summarized using n, mean, standard deviation, median, minimum, and maximum unless otherwise specified.

9.6.2 *Prior and Concomitant Medications*

[figure not shown]
Prior and concomitant medications, categorized by medication group and subgroup according to the World Health Organization (WHO) Drug Dictionary, will be summarized by treatment for the As-treated population. Medications with an end date prior to the first dose of study drug will be considered prior medications.

9.6.3 *Relevant Protocol Deviations*

Relevant protocol deviations are deviations that can have an impact on the primary efficacy endpoints. The impact of relevant protocol deviations on the primary efficacy results will be assessed by excluding subjects from the FAS to define the PPS in supportive analyses of the primary efficacy endpoints. Relevant protocol deviations to be considered regarding exclusion of subjects from the FAS will include the following:

- Subject was randomized but did not take any study treatment
- Subject failed to meet any study inclusion criteria but was randomized to receive study treatment
- Subject met a study exclusion criterion which may have an impact on the coprimary efficacy endpoints but was randomized to receive study treatment
- Subject was noncompliant with study treatment within the first 16 weeks of treatment; defined as <80% compliant with study treatment
- Subject took prohibited concomitant medication prior to Week 16
- Subject received treatment different than assigned treatment at any visit prior to Week 16

All subjects with relevant protocol deviations will be identified prior to the Week 16 database lock. Relevant protocol deviations will be summarized by treatment group and deviation category for the FAS population.

9.7 *Interim Analyses*

No interim analysis is currently planned.

9.8 *Analysis and Reporting*

An unblinded analysis of the data collected up to Week 16 will be conducted once all randomized subjects have either completed the placebo-controlled treatment period (ie, through Week 16) or have discontinued prior to Week 16. Details of these analyses will be provided in an SAP that will be finalized before the Week 16 database lock. A final database lock and analysis will occur after all subjects complete Week 52 or discontinue prior to Week 52.

